3.2.1 Definition of endpoint(s)

Part A

The ALSFRS-R is composed of 12 items across 4 subdomains of bodily function (bulbar, fine motor, gross motor, and breathing), with each item scored on an ordinal scale from 0 (total loss of function) to 4 (no loss of function). The total score of the ALSFRS-R ranges from 0 to 48, with a higher score indicating better function (1). Good reliability between face-to-face and telephone administration of the ALSFRS-R has been demonstrated (2).

Part B

The survival endpoint will be defined as the time to death or permanent assisted ventilation (>22 hours a day for >7 consecutive days), whichever comes first. CAFS is used to compare each study participant's outcome to others in the trial in a series of pairwise comparisons, based on function and survival (3). For each pairwise comparison, a study participant is assigned a score and then the summed scores are ranked for all participants. To calculate a participant's CAFS, each participant is compared individually to all other participants in the trial. The summary score for each participant is the sum of the comparisons (+1, 0, -1) against all other participants. For each pairwise comparison of patients, the participant who fares better earns a point, and the one who fares worse loses a point. In the case of a tie, no points are added or subtracted. If both participants die, the one surviving longer fared better; if only one survives then that participant fared better; and if both participants survive, the one with the smaller decline in ALSFRS-R from baseline fared better. If a participant discontinues early, comparison to each other participant uses time to death if the comparator died; otherwise, the comparison is based on the last ALSFRS-R time-point available for both participants. Once these scores have been calculated for all subjects, they are ranked, from lowest (died first) to highest (best ALSFRS-R outcome among those who survived), yielding the final CAFS score used as the endpoint. The average rank score is then calculated for each treatment group. A higher mean rank score indicates that participants in that treatment group, on average, fared better.

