3.2.2 Main analytical approach

Part A

The primary endpoint in Part A will be analyzed with the estimand defined according to the following attributes:

- Endpoint: Change from baseline in the ALSFRS-R total score to Week 24
- Treatment condition: SAR443820 will be compared to placebo
- Analysis population: ITT population
- Intercurrent events (IE):
 - The IMP discontinuation IE will be handled with the treatment policy strategy; The primary endpoint will be assessed based on all assessments irrespective of the IMP discontinuation
- Population-level summary: The primary endpoint will be analyzed using MMRM with change from baseline in ALSFRS-R total score up to Week 24 as response variable, and treatment, visit, randomization strata of the geographic region of the study site, ALS onset region (bulbar or other areas), use of riluzole (yes or no), use of edaravone (yes or no), use of the combination of sodium phenylbutyrate and taurursodiol (yes or no), treatment-by-visit interaction, disease duration (from first symptom onset to the screening visit), baseline ALSFRS-R score, baseline NfL, disease duration-by-visit interaction, baseline NfL-by-visit interaction and baseline ALSFRS-R score-by-visit interaction as covariates. If less than 10 participants in a randomization strata level, then the corresponding factor will not be included as a covariate in the MMRM model.

The least squares mean difference in the ALSFRS-R change from baseline at Week 24 between SAR443820 vs placebo, together with the p-value and the 95% CI for the difference, will be estimated from the MMRM model using weights for each stratum equal to the overall proportion of participants in each stratum (ie, “population weight”) by inclusion of the OBSMARGINS option in the LSMEANS statement. Plots of least squares means (\pm standard error) over time will be provided.

This model will be implemented using the SAS MIXED procedure with an unstructured covariance matrix to model the within-participant errors. Parameters will be estimated using the restricted maximum likelihood method. The denominator degrees of freedom will be estimated using the Kenward-Roger approximation. This model will provide baseline adjusted least-squares means estimates at Week 24 for SAR443820 and placebo, together with their corresponding standard errors and CIs. If this model fails to converge, the following variance-covariance structures will be tested in this order:

- Heterogeneous Toeplitz
- Heterogeneous AR(1)

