- Heterogeneous CS
- Toeplitz

- AR(1)
- CS.

[figure not shown]
The first (co)variance structure yielding convergence will be used as the primary analysis. When a variance-covariance structure other than unstructured is used, the denominator degree of freedom will be estimated using the between within method (DDFM=BW in SAS PROC MIXED) (4).

We assume a priori that change from baseline in the ALSFRS-R total score to Week 24 are normally distributed. Given the large sample size, the impact of violation of normality should not be great. In order to assess the impact of deviation from the normality assumption, a sensitivity analysis using rank analysis of covariance (ANCOVA) with the same covariates as for the MMRM analysis except visit and related interaction terms, will be performed to test the significance of the treatment effect.

Part B

CAFS score at Week 52 will be analyzed in the mITT population using the Wilcoxon-Mann-Whitney test to compare mean scores between the treatment groups at Week 52.

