For the time-to-event endpoints, baseline is defined as randomization. The time to event will be modeled by a Cox proportional hazards model. The covariates included in the model are treatment group, randomization strata of the geographic region of the study site, ALS onset region (bulbar or other areas), use of riluzole (yes or no), use of edaravone (yes or no), use of the combination of sodium phenylbutyrate and taurursodiol (yes or no), disease duration (from first symptom onset to the screening visit), baseline ALSFRS-R score and baseline NfL. The hazard ratio between SAR443820 and placebo, its 95% confidence interval and the p-value for comparing SAR443820 and placebo will be estimated from this model with robust variance estimation (9). Comparison between SAR443820 and placebo will also be assessed by a log-rank test stratified by randomization strata of the geographic region of the study site, ALS onset region (bulbar or other areas), use of riluzole (yes or no), use of edaravone (yes or no), use of the combination of sodium phenylbutyrate and taurursodiol (yes or no) and baseline NfL (< median baseline NfL or >= median baseline NfL). Kaplan-Meier (KM) plots of the cumulative incidence rate will be provided by treatment group to depict the course of occurrence of event over time. The proportion of participants with events at given time points (eg, Week 4, 8, 12, 16, 20, 24, etc.) and median time to event (if feasible) will be calculated using the KM estimates.

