3.3.1.3 Sensitivity analyses

CAFS endpoints in Part A and Part B

[figure not shown]
To assess the impact of baseline characteristics in the comparison of CAFS scores between treatment groups, a sensitivity analysis using a similar rank ANCOVA model to adjust for baseline prognostic factors in the mITT population as mentioned in [Section 3.2.3](#) will be performed at Week 24, Week 76 and Week 104, respectively.

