3.4.3 Comparison with external control

A matched analysis using data from historical clinical trial database (for example, PROACT) as a control will be conducted to demonstrate the superiority of SAR443820 on slowing down disease progression and prolonging survival over 104 weeks of treatment period.

Matching procedure

1. Pre-matching filtering: The participants in the historical clinical trial database will be filtered by the following factors that match our trial eligibility criteria and duration:
 - Age 18 – 80 years, inclusive
 - First ALS symptom onset ≤ 2 years
 - Baseline SVC (%) $\geq 60\%$
 - Baseline ALSFRS-R decline rate $\geq 0.5/\text{month}$
2. Propensity score matching: Propensity score matching seeks to balance the distributions of known prognostic covariates in treatment and control group to resemble what would occur had the treatment been randomly assigned. A logistic regression for the treatment group as the dependent variable is performed to obtain the propensity score with the abovementioned matching variables, using all the participants (planned for 174) randomized to the SAR443820 arm and the participants from the historical clinical trial database after filtering as described above. Each participant in the SAR443820 treated group will be matched 1:1 using the Mahalanobis distance to a participant in the historical clinical trial database. Matching will be performed with replacement.

To assess the success of the matching procedure, summary statistics of baseline matching variables will be presented and compared between the two treatment groups before and after matching to assess post-match balance.

Post-matching statistical analysis

Once the matching is performed, the comparison between participants who were randomized to SAR443820 and placebo arm generated from the historical trial database will be provided for the following endpoints using the similar analyses models as described for the primary and secondary endpoints in [Section 3.2.2](#) and [Section 3.3.1.2](#).

- Combined assessment of function and survival (CAFS) score at Week 52, Week 76, and Week 104
- Change from baseline in ALSFRS-R total score to Week 52, Week 76, and Week 104
- Time from baseline to the occurrence of either death or permanent assisted ventilation (>22 hour daily for >7 consecutive days) whichever comes first
- Time from baseline to the occurrence of death

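### The exploratory external-control comparison (SAP 3.4.3) has no variance rule for historical controls matched more than once, and still speaks of 104 weeks of treatment that the Part B pause rules out without interruption

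*SAP*

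**What the plan says.** SAP 3.4.3 plans a comparison with historical controls "to demonstrate the superiority of SAR443820 on slowing down disease progression and prolonging survival over 104 weeks of treatment period". The pool is filtered on age, time since symptom onset, SVC and ALSFRS-R decline rate. A logistic propensity score is fitted on these variables, and each participant in the SAR443820 arm (174 planned) is matched 1:1 by Mahalanobis distance. "Matching will be performed with replacement". Post-match balance is to be summarized. CAFS, ALSFRS-R change and the two survival endpoints are then analysed "using the similar analyses models as described for the primary and secondary endpoints" in 3.2.2 and 3.3.1.2.

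Those sections specify the following:

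- **MMRM (3.2.2).** The errors are correlated within participant only. Besides the randomization factors, the covariates include "disease duration (from first symptom onset to the screening visit), baseline ALSFRS-R score, baseline NfL, disease duration-by-visit interaction". Age, SVC and decline rate are not among them.
- **Cox (3.3.1.2).** The hazard ratio "will be estimated from this model with robust variance estimation", with no cluster unit named. A log-rank test, stratified by the randomization factors and median baseline NfL, is added.
- **CAFS (3.2.1, 3.2.2).** For the score, "each participant is compared individually to all other participants in the trial". "CAFS score at Week 52 will be analyzed in the mITT population" with a Wilcoxon-Mann-Whitney test.

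On the source of controls, Protocol 9.4.5 names one Phase 3 trial and says the analysis might be done. SAP 3.4.3 says it will be done, and names a database only as an example.

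On exposure, SAP 1.1 gives 24 weeks in Part A plus 80 weeks in Part B. It also reports the 5 December 2023 instruction to pause Part B dosing, after which Part A completers roll over without drug. The version history dates the first randomization to 28 April 2022 and SAP version 2 to 8 January 2024.

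**The concern.** Matching with replacement lets one historical control stand in for several participants. The matched file then holds 174 control rows but fewer than 174 distinct people, and the imported models contain nothing that recognizes the copies. Taken alone, this makes standard errors too small.

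A second effect works the other way. Matching makes the two groups alike on the four variables. If a model leaves the variation from those variables in its residual, the naive standard error includes variance that matching has already removed from the difference, and so is too large. Disease duration is in the MMRM and Cox models. Decline rate enters only indirectly, through duration and baseline ALSFRS-R; age and SVC do not enter. The Wilcoxon test adjusts for nothing, and the log-rank test is only stratified.

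The CAFS has a further gap: no rule says how two copies of one control score against each other.

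At stake is how an exploratory result is read, given that the section speaks of demonstrating superiority, including on survival. A Week 76 or Week 104 difference could also be reported as the effect of 104 weeks of treatment when it reflects assignment to an interrupted regimen.

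**Working it through.** **1. Planned figures.** 24 + 80 = 104 weeks, and 261 x 2/3 = 174. Both agree with the SAP.

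**2. Reuse alone.** Let w be a control's number of matches. The effective number of controls is ESS = (sum w)^2 / (sum w^2). The ratio of true to naive standard error is sqrt[(1/174 + 1/ESS) / (2/174)] = sqrt[(1 + 174/ESS)/2]. The true two-sided error at nominal 5% is 2[1 - Phi(1.96/ratio)].

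The documents give no pool size, so 200 to 2000 is an assumption. ESS comes from simulating nearest-neighbour Mahalanobis matching with replacement on four covariates, with pool and trial means equal or 0.25 SD apart.

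| Assumed pool | Unique controls | ESS | Mean maximum reuse | SE ratio | Error from reuse alone |
|---|---|---|---|---|---|
| 200 | 105-110 | 78-86 | 4.9-5.6 | 1.23-1.27 | 11.1-12.3% |
| 500 | 139-144 | 117-124 | 3.4-3.8 | 1.10-1.12 | 7.4-7.9% |
| 1000 | 155-158 | 140-145 | 2.7-3.0 | 1.05-1.06 | 6.2-6.4% |
| 2000 | 164-166 | 155-159 | 2.3-2.4 | 1.02-1.03 | 5.5-5.7% |

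Example: ESS = 86 gives sqrt[(1 + 2.023)/2] = 1.229; 1.96/1.229 = 1.595; error 11.1%.

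**3. Reuse together with partial adjustment.** Simulated error at nominal 5%, with no treatment effect and no correction for reuse. The ANCOVA is a one-visit stand-in for the MMRM. It and the Cox model adjust for two of four independent matching variables, as a proxy for duration entering directly and decline rate indirectly. The Wilcoxon test is unadjusted.

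| Assumed pool | ANCOVA (4000 runs, R2 0.10-0.40) | Cox, row-level robust (2000 runs, 45% events assumed) | Wilcoxon on CAFS (1500 runs) |
|---|---|---|---|
| 200 | 7.4-11.8% | 10.1-10.3% | 7.3-10.1% |
| 500 | 4.2-7.8% | 5.3-6.2% | 3.9-6.3% |
| 1000 | 3.4-6.2% | 4.9-6.2% | 3.2-4.9% |
| 2000 | 2.4-5.3% | 3.7-4.5% | 2.6-3.8% |

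Monte Carlo error for the ANCOVA is about 0.7 points. A separate run with decline rate derived from baseline score and duration gave 8.7-9.8% at 200 and 3.3-4.7% at 2000. When the outcome is unrelated to the matching variables, the offset vanishes. Naive error was then 5.5-14% over pools of 200 to 3000 and mean differences up to 0.5 SD.

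**4. What repairs it.** Clustering on the control alone, with two variables adjusted, gives 2.1-5.0% (ANCOVA), which overcorrects. Clustering plus all four variables gives 4.2-6.0% (ANCOVA), 4.5-6.2% (Cox) and 4.3-5.5% (rank ANCOVA on CAFS, copies tied). Unique controls weighted by match count, with sandwich variance and the four variables, gave 4.6-6.5% across pools in the derived-slope run.

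**5. Exposure.** 28 April 2022 to 5 December 2023 is 586 days; 586/7 = 83.7 weeks. The first participant was 104 - 83.7 = 20.3 weeks short at the pause and would have reached Week 104 on 25 April 2024. Completing 104 weeks before the pause needed a start by 7 December 2021, before anyone was randomized. SAP version 2 followed the pause by 34 days.

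**The case against.** The comparison is exploratory, lies outside the testing hierarchy of SAP 3.5, and has a balance check. The word similar leaves room to cluster. All of this stands and keeps the grade low, but room to cluster is also room not to, and the choice should be fixed before results are seen.

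The error rates rest on assumed pools, on raw-covariate Mahalanobis matching and on a one-visit model. That also stands. SAP 3.4.3 fits a propensity score as well, and matching on it could increase reuse.

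The pause is disclosed in SAP 1.1, resumption is left open, and 3.3.1.2 states treatment policy for the Part B secondary endpoints. This is correct, so the exposure half is about description. Resumed dosing would still be interrupted. The treatment-policy statement points to Table 2, which covers Part A only.

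A reader might infer three stronger points that the documents do not support:

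- **That the tests are always liberal.** In a large pool they can be conservative.
- **That no sensitivity analysis would reveal the problem.** SAP 3.4.2 excludes them for tertiary endpoints, but the outcomes here are Part B primary or secondary endpoints. Section 3.2.3 also shows a heading without visible text, so absence cannot be established.
- **That Week 104 cannot be analysed.** Follow-up visits continue to be encouraged, so the data can exist.

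**Conclusion.** The point holds as an improvement to consider. As written, the p-values and intervals against historical controls have no controlled error rate. One-visit naive error at nominal 5% is about 7-12% at a pool of 200, 4-8% at 500, 3-6% at 1000 and 2-5% at 2000. Inflation is largest in a small pool but not confined to it. The figures depend on the assumed pool size, covariate strength, overlap and matching metric.

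The exposure statement needs no assumption about accrual: the SAP's own dates cap uninterrupted dosing at 83.7 weeks. What fails is the description as 104 weeks of treatment, not the Week 104 comparison itself. The Part A primary conclusion is unaffected.

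**What to change.** In SAP 3.4.3:

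1. Enter each unique historical control once, weighted by its number of matches. For the MMRM use empirical (sandwich) variance by participant with between-within degrees of freedom; for survival use a weighted Cox model with robust variance. This amounts to clustering on control ID and avoids duplicate subjects in the unstructured matrix. Between-within is already the fallback in 3.2.2; empirical variance for the MMRM would be new.
2. Add age, SVC and pre-study slope to the disease duration already in these models.
3. For CAFS at Weeks 52, 76 and 104, score copies of one control as ties. Take the p-value from a rank ANCOVA with the matching variables and variance clustered on control ID. SAP 3.3.1.3 already plans "a sensitivity analysis using a similar rank ANCOVA model to adjust for baseline prognostic factors in the mITT population", but its visible text lists Weeks 24, 76 and 104, so Week 52 should be named.
4. Do not report an unweighted log-rank p-value; use the weighted robust Cox test.
5. Report the number of unique controls, the effective number and the maximum reuse.
6. Describe the comparison as over follow-up through Week 104 under treatment policy. Name the Part B pause as an intercurrent event handled by that strategy, and reconcile 3.4.3 and the Part B text with SAP 1.1. All visits stay in.

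The cost is a short SAP edit and a short extra program, mainly for CAFS. Intervals widen if the pool is small: with all four variables adjusted, the true standard error is 1.23-1.30 times the naive one at 200 and 1.01-1.04 times at 2000.

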3.5 MULTIPLICITY ISSUES

To control the Type 1 error rate for the study, a hierarchical testing procedure will be applied at a 2-sided 5% significance level for primary and selected secondary endpoints in Part A, ie, each hypothesis will be formally tested only if the preceding one is significant at the 5% level. If

SAR443820 is significant for the primary endpoint in part A, a selective set of secondary endpoints in Part A will be tested following the hierarchical testing procedure shown below:

- CAFS score at Week 24
- Change from baseline in ALSAQ-5 to Week 24
- Change from baseline in serum NfL to Week 24
- Change from baseline in SVC to Week 24
- Change from baseline in megascore to Week 24

3.6 SAFETY ANALYSES

All safety analyses will be performed on the safety population as defined in [Section 2](#), unless otherwise specified, using the following common rules:

- The analysis of the safety variables will be essentially descriptive, and no testing is planned.
- Safety data in participants who do not belong to the safety population (eg, exposed but not randomized) will be provided separately.

In Part A safety analysis, the safety analyses will be carried out with patients by the actual treatment received, irrespective of the treatment the patient has been randomized to.

Part A + Part B Safety Analyses

For categorical safety measures, such as AE, PCSA, shift summaries, data throughout both Part A and Part B will be summarized in three groups:

- Placebo/SAR443820 group includes participants who actually received placebo in Part A and SAR443820 in Part B. For participants in this group, only the data during SAR443820 exposure in Part B will be summarized. The baseline will be defined as the last available value prior to the first dose of SAR443820 in Part B.
- SAR443820/SAR443820 group includes participants who actually received SAR443820 in Part A, regardless of whether they entered Part B. For participants in this group, all data during SAR443820 exposure will be summarized. The baseline will be defined as the last available value prior to the first dose of the study intervention (same baseline defined for Part A in [Section 3.1](#)).
- Overall SAR443820 group includes participants from Placebo/SAR443820 group and SAR443820/SAR443820 group.

For continuous safety measures collected at longitudinal time point, such as labs and vital signs, data throughout both Part A and Part B will be summarized in two groups:

- Placebo/SAR443820 group includes participants who actually received placebo in Part A, regardless of whether they entered Part B. For participants in this group, all data during the on-treatment period of Part A and Part B will be summarized at each

protocol scheduled visit. The baseline will be defined as the last available value prior to the first dose of study intervention (same baseline defined for Part A in [Section 3.1](#)).

- SAR443820/SAR443820 group includes participants who actually received SAR443820 in Part A, regardless of whether they entered Part B. For participants in this group, all data during the on-treatment period of Part A and Part B will be summarized at each protocol scheduled visit. The baseline will be defined as the last available value prior to the first dose of study intervention (same baseline defined for Part A in [Section 3.1](#)).

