- i* A full physical examination will be performed at the screening visit, and a brief physical examination will be performed at all other visits. The skin and lymph nodes need to be checked at each site visit.
- j* Vital signs include blood pressure, heart rate, respiratory rate, and temperature.
- k* Postdose vital signs should be measured at least 10 minutes after the second PK sample collection (recommended to be measured within 10 to 30 minutes after the second PK sample collection).
- l* The "Since Last Visit" version of the C-SSRS will be used.
- m* A full neurological examination will be performed at the screening visit, and a brief neurological examination pertaining to cranial nerves, coordination/cerebellar function, reflexes, and motor function will be performed at other visits.
- n* Substances include drugs of abuse, alcohol, tobacco, and caffeine.
- o* Only in female participants, if needed to establish menopausal status.
- p* Only liver chemistry monitoring will be conducted, which includes testing of alanine transaminase (ALT), aspartate aminotransferase (AST), bilirubin direct, bilirubin total and alkaline phosphatase.
- q* Optional one-time blood draw for DNA analysis can be completed at either Week 2 or Week 4 visit.
- r* The muscles measured include both upper-limb and lower-limb muscle groups. Bilateral hand grip will be measured using a Jamar grip dynamometer and all other muscles included in this study will be measured using a handheld dynamometer.
- t* The IMP can be taken under either fasting or non-fasting condition.
- u* Two samples for PK will be collected at this visit, 1 within 15 minutes to 1 hour and another within 1 to 3 hours after the morning dose of IMP. There will be at least 45 minutes between the 2 samplings.
- v* One sample for PK will be collected within 1 hour before the morning dose of IMP.
- w* One sample for PK will be collected within 15 minutes to 3 hours after the morning dose of IMP.
- x* The cytokines measured in this study include IFN- $\gamma$ , IL-1 $\beta$ , IL-2, IL-4, IL-6, IL-8, IL-10, IL12p70, IL-13, and TNF- $\alpha$ . The chemokines measured in this study include eotaxin-1, eotaxin-3, TARC, IP-10, MIP1 $\alpha$ , MIP1 $\beta$ , MCP1, and MCP4.
- y* This assessment will not be conducted in China (see Appendix 8 [[Section 10.8](#)]).

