3 STATISTICAL ANALYSES

3.1 GENERAL CONSIDERATIONS

In general, continuous data will be summarized using the number of observations available, mean, standard deviation (SD), median, interquartile range (Q1, Q3), minimum, and maximum.

Categorical and ordinal data will be summarized using the count and percentage of participants.

Efficacy data will be analyzed in the ITT population, except CAFS endpoints in Part A and Part B will be analyzed in the mITT population. Safety data will be analyzed in the safety population, unless specified otherwise.

In Part A, baseline values are defined as follows. The baseline values of NFL, CHI3L1, the cytokine and chemokine panel in serum, sTREM2 in plasma and $p75^{ECD}$ in urine, are defined as the average value from samples collected at the screening visit and at Day 1 prior to the first dose of the study intervention. For the C-SSRS, the baseline value will be the worst assessment between the past 6 months evaluation at screening and the since last visit evaluation on Day 1. For the other efficacy and safety assessments, the baseline values are defined as the last available value prior to the first dose of study intervention. For participants randomized but not treated, the baseline value is defined as the last available value before randomization. Unless otherwise indicated, 2-sided p-values and 95% confidence intervals [CI(s)] will be provided for efficacy assessment of treatment differences. Unless otherwise specified, analyses will be performed by treatment group (and overall for baseline and demographics characteristics).

Efficacy analyses in Part B will be conducted accumulatively according to the treatment group allocated by randomization in Part A (ie, Placebo/SAR443820 versus SAR443820/SAR443820). Baseline values defined above for Part A will be used as the baseline in the efficacy analyses for Part B, unless otherwise noted. Safety analyses in Part B are stated in [Section 3.6](#).

Observation period

The observation period for safety will be divided into 4 segments:

- The **pre-treatment period** is defined as the period up to first investigational medicinal product (IMP) administration.
- The **on-treatment period** (ie, treatment-emergent (TE) period) **for the Part A** is defined as the period from the first IMP administration to the earliest of 1) last IMP administration + 14 days, 2) first IMP in Part B, 3) death date, or 4) last contact date.

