3.6.3.2 Analysis of suicidality assessment

The number (%) of participants with suicidal ideation, suicidal behavior, and self-injurious behavior without suicidal intent based on the C-SSRS during treatment will be summarized. A shift table for baseline versus during treatment responses in Part A and Part A + Part B will be provided according to the categories of no suicidal ideation or behavior, suicidal ideation and suicidal behavior.

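### The Part A + Part B C-SSRS shift table uses a roughly 6-month worst-value baseline for SAR443820/SAR443820 but a single form covering about 8 weeks for Placebo/SAR443820, so new-onset ideation means different things in adjacent and pooled columns (minor)

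*SAP*

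**What the plan says.** SAP 3.6.3.2 states: "A shift table for baseline versus during treatment responses in Part A and Part A + Part B will be provided". The categories are "no suicidal ideation or behavior, suicidal ideation and suicidal behavior", so all levels of ideation share one row. The section gives no baseline rule of its own.

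The rule comes from SAP 3.6: "For categorical safety measures, such as AE, PCSA, shift summaries, data throughout both Part A and Part B will be summarized in three groups". The three groups are:

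- **Placebo/SAR443820.** Only data during Part B exposure count. "The baseline will be defined as the last available value prior to the first dose of SAR443820 in Part B".
- **SAR443820/SAR443820.** All data during SAR443820 exposure count. The baseline is the last available value "prior to the first dose of the study intervention (same baseline defined for Part A in" Section 3.1).
- **Overall SAR443820.** This pools the two.

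For most assessments the Section 3.1 baseline is the last value before dosing, but C-SSRS has its own rule: "the baseline value will be the worst assessment between the past 6 months evaluation at screening and the since last visit evaluation on Day 1". The sentence in SAP 3.1 that carries Part A baselines into Part B covers efficacy analyses only.

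Protocol 1.3.1 schedules the C-SSRS at screening, Day 1 and Weeks 2, 4, 8, 16 and 24. From Day 1 on, "The 'Since Last Visit' version of the C-SSRS will be used" (footnote l). Footnote a places the end-of-Part-A assessments before the first open-label dose.

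**The concern.** A shift table is there to separate ideation that arises on drug from ideation already present. Here the two groups define already present differently. The SAP took C-SSRS out of the last-value rule in Section 3.1, but did not carry that exception into the Placebo/SAR443820 rule in Section 3.6.

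Take a placebo participant who reports ideation at Week 4, none at Week 24, and ideation again in Part B. That participant is tabulated as moving from none to ideation. A SAR443820/SAR443820 participant with the same history inside the 6-month window is tabulated as having ideation at baseline. The pooled column then adds the two definitions together. Protocol 8.2.7 gives the drug's passage across the blood-brain barrier as context for monitoring suicidality, so this table is likely to be read.

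**Working it through.** The plan gives no ideation rate or expected shift count, so there is no figure to reproduce. The check traces the definitions and then sizes the effect under stated assumptions.

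**1. Look-back by group**

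| Group | Baseline form(s) | Look-back |
|---|---|---|
| SAR443820/SAR443820 | Worst of the 6-month screening form and the Day 1 form | About 26 weeks, plus up to 4 weeks of screening: 26 to 30 weeks |
| Placebo/SAR443820 | Week 24 form only | Week 16 (Day 113) to Week 24 (Day 169): 56 days = 8 weeks |

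With the ±3-day visit windows, the second look-back runs from 50 to 62 days, or 7.1 to 8.9 weeks. It is longer if the Week 16 form is missed. Weeks 20 to 23 carry no C-SSRS. If the form is taken to mean the last visit of any kind, the look-back could be as short as 1 week (Week 23, Day 162).

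**2. Direction**

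On one history, the worst value over a longer window cannot be milder than the most recent form inside it. The shorter baseline can therefore only move people into the no-ideation row, and so can only add shifts from none to ideation.

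**3. Size**

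Assume a constant rate of brief ideation, with 6-month probability *p* (5%, 10% or 20%; assumed, not in the documents). The probability over *t* weeks is 1 − (1 − *p*)^(*t*/26). An extra shift needs both of the following:

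- ideation inside 26 weeks but not in the last 8, with probability *p* − *p*₈;
- ideation during the 80 planned weeks of Part B, with probability *P*₈₀.

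Extra shifts = 87 × (*p* − *p*₈) × *P*₈₀. The 87 is the planned placebo arm.

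| *p* | *p*₈ | 87 × (*p* − *p*₈), relabelled baselines | *P*₈₀ | Extra shifts |
|---|---|---|---|---|
| 5% | 1.6% | 3.0 | 15% | 0.4 |
| 10% | 3.2% | 5.9 | 28% | 1.6 |
| 20% | 6.6% | 11.6 | 50% | 5.8 |

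Applying the 20% drop-out used in the sample-size section multiplies the last column by 0.8, giving 0.3, 1.3 and 4.6. The Part B dosing pause lowers both the group size and *P*₈₀ further.

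If ideation instead clusters in a few prone individuals (gamma-distributed rates, shape 0.2), the shares shifting with an 8-week and a 26-week look-back are:

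- at *p* = 5%: 11.15% and 9.53%, a difference of 1.62 points, × 87 = 1.4 extra shifts;
- at *p* = 10%: 17.67% and 13.54%, a difference of 4.13 points, × 87 = 3.6 extra shifts.

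**4. Net comparison of the two groups**

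For *p* from 2% to 10%, and heterogeneity from none to shape 0.2:

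| Comparison, Placebo/SAR443820 to SAR443820/SAR443820 | Ratio of shift shares |
|---|---|
| 8- versus 26-week look-back, both counted for 80 weeks | 1.01 to 1.31 |
| 8- versus 30-week look-back, both counted for 80 weeks | 1.02 to 1.37 |
| As planned: 8-week look-back and 80 weeks versus 26-week look-back and 24 + 80 = 104 weeks | 0.79 to 1.11 |
| Common 8-week look-back, 80 versus 104 weeks | 0.78 to 0.87 |

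The look-back pushes the ratio up and the unequal exposure pushes it down. The planned ratio can fall on either side of 1.

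**The case against.** The strongest reply is that little depends on this table. SAP 3.6 makes safety analyses descriptive, with no testing. SAP 3.6.3.2 also reports ideation and behavior during treatment without conditioning on baseline. The Part A shift table, which holds the placebo comparison, uses one C-SSRS baseline rule for both arms. In the Part A + Part B table both groups are on SAR443820. All of this stands, and it limits the matter to interpretation of one output.

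Three further points have partial force:

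- **Entry criteria.** E 06 excludes category 4 or 5 ideation and attempts within 6 months. Lower categories can still enter, and they share the single ideation row.
- **Wording.** SAP 3.6 describes the SAR443820/SAR443820 baseline as a last available value. Read literally, that is the Day 1 form, looking back at most 4 weeks, and the 6-month contrast disappears. The same sentence equates it with the Section 3.1 baseline, which has an explicit C-SSRS rule, so the worst-value reading is the better one. The ambiguity still needs correcting.
- **The remedy.** Repeated prospective forms may pick up more ideation than one 6-month recall, so a worst-of-Part-A baseline is only approximately comparable.

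A reader might infer that shifts will look more frequent in Placebo/SAR443820. The documents do not support that, because SAP 3.6 also counts on-treatment time unequally, in the opposite direction, and the pause alters both durations. A reader might also take the 3, 6 or 12 relabelled baselines as false shifts. They are not: a relabelled participant adds a shift only if ideation occurs during Part B exposure. Nor is 87 the group size, since SAP 3.6 admits only participants who actually received SAR443820 in Part B.

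**Conclusion.** The asymmetry is in the text, and no other section removes it. Shifts from none to ideation in Placebo/SAR443820, and in the Overall SAR443820 column, are inflated relative to a like-for-like baseline. The conclusion goes no further than that, since the ordering of the two groups cannot be predicted from the plan.

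The likely number of extra shifts is small: about 0.4, 1.6 or 5.8 at assumed 6-month prevalences of 5%, 10% or 20%, under a constant rate, 87 participants and 80 weeks. Clustering of ideation in the same people raises these figures somewhat; drop-out and the pause lower them. The conclusion assumes that since last visit means since the last C-SSRS, and that the pointer to Section 3.1 governs the SAR443820/SAR443820 baseline. Severity is minor.

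**What to change.** In SAP 3.6, under the Part A + Part B rules for categorical measures:

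1. State that for C-SSRS in Placebo/SAR443820 the baseline is the worst response over all assessments from Day 1 through the pre-dose Week 24 assessment. The Day 1 form reaches back to screening, so this covers 24 weeks plus up to 4, or 24 to 28 weeks, against 26 to 30 in the other group.
2. For C-SSRS in SAR443820/SAR443820, replace the last-available-value wording with a direct reference to the worst-value rule in Section 3.1.
3. Footnote the table: the look-backs are only approximately comparable (repeated forms versus one 6-month recall), and on-treatment time differs between the groups. The baseline change does not remove the exposure difference.

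The cost is two sentences and a footnote. All the forms are already scheduled in Part A, and no visit, participant procedure or other analysis changes.
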